7.1.6. Communication platform

The control algorithm resides on a CE-marked Samsung Galaxy A5 2017 Android phone (figure 8, #1). To secure data the Android phone do not have a SIM card and no Wi-Fi connection is allowed. All codes and commands are executed on the Android phone. The Android phone is connected to the Dexcom G6 CGM transmitter (figure 8, #2) via a Bluetooth Low Energy (BLE) connection and receives a new glucose value every 5 min. The glucose values serve as input to the controllers. The controller output, i.e. the insulin or glucagon dose to be delivered, is communicated from the Android phone to the pumps (figure 8, #3 and #4) via BLE. The Android phone handles all the BLE communications. Data are stored locally on the Android phone. After the trial the data are accessible for researchers by connecting a private computer located at the hospital to the Android phone using USB (figure 8, #5).

[figure not shown]

Figure 8: Deployment diagram of the complete set up of the closed-loop system

If the BLE connection between the communication platform (the CGM receiver) and the CGM is temporarily lost, i.e. no glucose value is transferred; insulin estimations will be based on the controller prediction. The attending physician evaluates safety of the insulin dosing and is always able to overrule the closed-loop system.

Our technical collaborators from DTU are responsible for training the investigators in the use of the communication platform prior to study start. A person from DTU will be present at the research lab during study phase 1 to assist in overcoming any start-up difficulties. During study phase 2, the person can be contacted by telephone if any difficulties arise. For this study all device handling is managed by the investigators and no subject training is needed.

In order to start the system, the two DanaRS pumps and the DexCom G6 transmitter should be paired to the Samsung Galaxy A5 2017, participant specific information (study id and controller variables) should be entered, and finally device connection and communication with controller unit should be verified. The investigators will be trained in this procedure before study start. For this study all device handling is managed by the investigators and accordingly no subject training is needed.

Any device deficiencies detected during the study will be reported to the manufacturers of the devices involved.

7.2. Study medication

7.2.1. Glucagon, GlucaGen®, Novo Nordisk, ATC code H04AA01

Please refer to the medication summary attached for further details including adverse reaction profile (section 4.8).

The product is commercially available by prescription and indicated for participants with T1D. The recommended glucagon dose for children above 10 years old living and acutely suffering from severe hypoglycemia is 1 mg administered as a subcutaneous or intramuscular bolus. The administration

may be repeated once if lack of clinical response. In this study, glucagon is delivered as microboluses up to every five minutes and the dose size is based on the current blood glucose value. It is expected that in this study the total daily glucagon dose will not exceed 1.0 mg per day. The glucagon pump is filled with freshly reconstituted glucagon 1 mg/ml every 13 hours, i.e. before study start and at 14:00 (other groups have reported uncomplicated use of glucagon with reconstitution intervals of up to 24 hours).

The effects of glucagon are not expected to extend beyond the course of the actual study days. Accordingly, no post-study follow-up is planned, but participants are encouraged to contact the sponsor if they experience or suspect any adverse events to the study medication in the 24 hours following discharge from the research unit. This also applies to participants who discontinue study participation.

Glucagon is ordered via the hospital's pharmaceutical service associated with the pharmacy of the Capital Region. Batch number, date of expiration and the amount used to fill the pump is noted in the participant eCRF.

7.2.2. Insulin, Fast-acting insulin aspart, FiAsp®, Novo Nordisk, ATC code A10AB05.

Please refer to the medication summary attached for further details including adverse reaction profile (section 4.8).

The product is commercially available by prescription and indicated for participants with T1D. Insulin is delivered as microboluses up to every five minutes and the dose size is based on the current blood glucose value. It is expected that the total daily insulin dose will be similar to the participant's usual daily dose. In general, the total daily dose is dependent on food intake, exercise and health status. The method of insulin delivery (microboluses vs. continuous infusion and automated versus participant-driven control) differs from current practice, however, otherwise participants receive insulin in accordance with usual standard of care, i.e. we try to achieve near-normalization of blood glucose values. The insulin pump is filled with fast-acting insulin aspart 100 IE/ml before study start.

Fast-acting insulin aspart is ordered via the hospital's pharmaceutical service associated with the pharmacy of the Capital Region. Batch number, date of expiration and the amount used to fill the pump is noted in the participant eCRF.

7.2.3. Saline (not a study medication)

On the single-hormone study days, a 'dummy' pump is filled with isotonic saltwater (sodium chloride 9 mg/dl). However, the pump will be set to not infuse any saltwater during the study period. The reason for the pump to be filled but not infuse saltwater is that the pumps will alarm if there are no solution in the infusion and/or cartridge. Furthermore, we need to mimic that we are refilling the cartridge and infusion sets as we do for glucagon in order to keep the blinding for the participants. The "dummy" pump will only serve as a placebo to glucagon and will not follow an algorithm. Therefore, sodium chloride is considered a study tool and not a study medication.

8. Study outcomes

8.1. Phase 1

No specific endpoints. In this phase, we explore the operability of our systems with emphasis on the safety issues.

8.2. Phase 2

8.2.0. Primary outcome between single- and dual-hormone closed-loop system

- Percentage of time with glucose values < 3.9 mmol/l as measured by CGM*

8.2.1. Secondary outcomes between single- and dual-hormone closed-loop system

8.2.1.1 Carbohydrate outcomes

- Number of carbohydrate interventions to treat hypoglycemia*

8.2.1.2. Glucose outcomes

- Percentage of time with glucose values in the range 3.9-10.0 mmol/l measured by CGM and YSI*
- Percentage of time with glucose values < 3.9 mmol/l as measured by YSI*
- Percentage of time with glucose values in the range > 13.9 mmol/l measured by CGM and YSI*
- Percentage of time with glucose values < 3.0 mmol/l as measured by CGM and YSI*
- Mean blood glucose value measured by CGM and YSI*
- Number of hypoglycemic episodes < 3.9 mmol/l on CGM an YSI
- CGM glycemc variability measured as SD and CV*
- Composite outcome: Percentage of participants achieving (1) time in range (3.9-10) > 70 %, (2) time in alert hypoglycemia (<3.9 mmol/l) < 4 %, and (3) time in clinical hypoglycemia (<3.0 mmol) < 1% as measured by CGM and YSI*

8.2.1.3. Insulin and glucagon dosages

- Total insulin dose
- Total glucagon dose
- Number of manual insulin boluses

8.2.1.4. Adverse events

- Number of adverse events (event if visual analog scale (0-100) increase >10 from baseline) for
 - Nausea
 - Headache
 - Palpitation
- Number of vomits

8.2.1.5. Other:

- Difference between actual and participant-estimated CHO content in meals
- Mean Borg scale level during exercise

- Physical activity intensity measured by ActiGraph GT9X Link
- Sleep efficiency measured by ActiGraph GT9X Link

Means, medians, percentages, standard deviations, ranges, interquartile ranges and 95% confidence intervals will be calculated for descriptive analyses. All inferential outcome analyses compare single-hormone with dual-hormone closed-loop glucose control using paired t-test for normally distributed data and Wilcoxon signed-rank test when data cannot be assumed to be normally distributed.

* An asterisk indicates that the outcome will be calculated for the whole study period as well as for the following intervals: dinner (19:00-23:00), night (23:00-08:00), breakfast (08:00-12:00), lunch + snack (12-16:30), and exercise session (16:30-19:00).

9. Statistical considerations and power calculation

9.1. Phase 1

Phase 1 is a feasibility study in which we explore operability of our system with special emphasis on safety issues. Reaching statistical significance is not a goal. We choose to include a maximum of four participants with T1D in this phase.

9.2. Phase 2

To be able to detect a difference in percentage of time with glucose values < 3.9 mmol/l (primary outcome) of 2.3 %-points (approximately 30 minutes) with 90% power, a 5%-significance level, and a presumed 3.0 %-points standard deviation, 20 participants should be included in the study (2-sided test). The sample size calculation is partly based on data obtained from our adult study; however, we expect higher variation due to pubertal status.

Participants who drop out of the study will be replaced such that the total number of participants who have completed a single- and a dual-hormone closed-loop study is 20. Only data from participants who have completed a full single- and a full dual-hormone study session will be included in the analysis comparing the two control types. More than 80% of possible sensor values from each study session are required to be included in the analysis. Furthermore, data from completers and non-completers will be stated in the final report.

For every carbohydrate rescue during the study, 30 minutes of the time in range is allocated to time in hypoglycemia and will be accounted for in the primary analysis. A paired student's t-test will be used to compare the outcomes if data are normally distributed. Otherwise, a Wilcoxon Signed Rank test is be used. In order to account for missing values and adjusting for different factors, a repeated measurement ANOVA will be used with the outcome and adjusting factors as fixed effects and the intercept as a random effect. Bonferroni adjustments will be applied for non-specified outcomes.

Based on previous experience from this type of study we expect a very low drop-out rate, $< 10\%$.

Therefore, a maximum of 24 participants are needed for this project that includes phase 1 (N=4) and phase 2 (N=20).

If it turns out that deviations from the statistical plan described above are necessary, the Danish Health and Medicines Authority, the Regional Scientific Ethics Committee and the GCP-unit will be informed. The original statistical plan as well as the new strategy will be reported in the publication of study results.

10. Safety

For safety reasons, at least one study personnel will always be present during the clinical study.

10.1 Hypoglycemia management:

Hypoglycemia will be managed according to the standard operating procedures (SOP_Dysglycemia). A hypoglycemia episode is defined as one plasma glucose value < 3.0 mmol/l. In the event of a hypoglycemic episode, the attending physician will take immediate action to raise the blood glucose by providing the participant with oral carbohydrate. The treatment will be repeated if the hypoglycemia has not resolved within 15 minutes. Repeated YSI measurement will be performed every 5 minutes until BG is > 3.9 mg/dl (SOP_Dysglycemia).

If at any point during the study the participant experiences symptoms of hypoglycemia and requests oral carbohydrate, a blood sample for plasma glucose determination will be drawn. Irrespective of the plasma glucose value the participant will be treated with oral carbohydrate. However, repeated YSI measurements will only be measured if < 3.9 mmol/l.

If at any point during the study the participant experiences a severe hypoglycemic event, i.e. the participant is unable to take oral CHO, intravenous glucose will be administered via the sampling cannula and the study will be terminated.

10.2. Hyperglycemia management:

Hyperglycemia will be managed according to the standard operating procedures. If an YSI blood glucose value exceeds 14.0 mmol/l or if YSI blood glucose values are > 12.0 mmol/l for > 2 hours, blood ketones will be measured using a Precision Xceed ketone meter (Freestyle Precision B-ketone, Abbott, Abbott Park, Illinois). If the ketone level is ≥ 0.6 mmol/l, the closed-loop system will be checked for any malfunction and any problems will be corrected (SOP_Dysglycemia). Ketone measurements will be repeated every 15 minutes until the ketone level is < 0.6 mmol/l. However, if hyperglycemia occurs within 2 hours postprandially, no ketone or other actions must be done.

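### Session order is randomised, but the planned paired tests have no period term and the model's fixed effects are not named, so period adjustment is not assured

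*Combined protocol and SAP*

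**What the plan says.** Section 4.2 describes phase 2 as a randomised, single-blinded cross-over, and section 6.1 (Randomization) fixes the order of the two periods by block randomisation with random blocks of 2 and 4.

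The analysis is given in two places. The paragraph closing section 8.2.1.5 covers all inferential comparisons, "using paired t-test for normally distributed data and Wilcoxon signed-rank test when data cannot be assumed to be normally distributed". Section 9.2 repeats this: a paired "t-test will be used to compare the outcomes if data are normally distributed", and "Otherwise, a Wilcoxon Signed Rank test is be used". Section 9.2 then adds a model, meant to handle missing data and covariates: "a repeated measurement ANOVA will be used with the outcome and adjusting factors as fixed effects and the intercept as a random effect". It does not list the factors or say whether the model or the paired test is primary. Neither section mentions a period or sequence effect.

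Only participants who complete both sessions are analysed. Drop-outs are replaced until 20 have completed, with no rule on which sequence a replacement follows. On attrition, the authors write "we expect a very low drop-out rate", below 10%.

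**The concern.** In a two-period cross-over, the outcome can differ between the first and second visit whatever the treatment, for example through familiarity with the clinic or the procedures. Each participant's dual-minus-single difference then contains the period effect, with a plus sign in one sequence and a minus sign in the other.

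A paired test that ignores sequence has two weaknesses. With equal sequences the period effect cancels from the mean difference but stays in its variance, so the test becomes conservative, the interval wider and the power lower. With unequal sequences the cancellation is incomplete, and that trial's estimate moves by a fraction of the period effect.

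The model could have covered this, but as written it lists the dependent variable as a predictor and leaves the covariates open. Period may or may not be among them, and the choice could be made after the data are seen.

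**Working it through.** **Inputs.** From section 9.2: difference d = 2.3 points, SD 3.0 points, 90% power, two-sided 5%, N = 20. From section 6.1: random blocks of 2 and 4. Assumed, because the documents do not give them: a period effect p (second visit minus first) of 0, 0.5, 1 or 2 points, a 1:1 sequence ratio, and drop-out unrelated to sequence.

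**The plan's own figure.** A paired t-test with SD of the differences 3.0 and n − 1 df (noncentral t) gives 88.5% power at n = 19 and 90.2% at n = 20. N = 20 is reproduced and is not in dispute.

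**Model.** Participant i has difference D_i = d + p·s_i + e_i. Here s_i = +1 if the dual-hormone session is second and −1 if it is first, and e_i has SD σ. Let b = (n1 − n2)/20, where n1 and n2 count the two sequences.

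- Paired t: the mean of D is centred on d + b·p. The sum of squares over σ² is noncentral chi-square with 19 df and noncentrality 20·p²·(1 − b²)/σ². At 10/10 and p = 1 this is 20·1/9 = 2.22.
- Adjusted: half the between-sequence difference in mean period differences, with SE = σ·√[(1/n1 + 1/n2)/4] and 18 df. At 10/10 the SE is 3.0·√(0.2/4) = 0.671. The result does not depend on p.

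**(a) SD 3.0 excludes period variation, 10/10 completers**

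| p (points) | Paired-t power | Adjusted power | Paired-t type I error | Mean 95% CI half-width, paired | Same, adjusted |
|---|---|---|---|---|---|
| 0 | 90.2% | 90.0% | 5.0% | 1.39 | 1.39 |
| 0.5 | 89.6% | 90.0% | 4.7% | 1.41 | 1.39 |
| 1 | 88.0% | 90.0% | 3.9% | 1.46 | 1.39 |
| 2 | 80.5% | 90.0% | 1.9% | 1.68 | 1.39 |

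Adjustment breaks even at p = 0.29 points.

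**(b) SD 3.0 already includes period variation, 10/10.** Then σ = √(9 − p²·20/19), that is 3.00, 2.96, 2.82 and 2.19 at the four values of p. Paired-t power is 90%, 90%, 91% and 96%; adjusted power is 90%, 91%, 93% and 99%. The break-even is again 0.29 points. The documents do not say which case applies, only that "The sample size calculation is partly based on data obtained from our adult study".

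**(c) 11/9 completers, SD as in (a).** Now b = 0.1, so the unadjusted estimate shifts by 0.1 points at p = 1 and 0.2 at p = 2, in either direction. Paired-t power at p = 1 is 91% or 85% by direction, and at p = 2 it is 87% or 72%. Adjusted power is 89.7%. Averaged over directions, the break-even is 0.45 points.

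**How likely is imbalance?** In 60,000 simulated allocation lists, with each replacement taking the next allocation, an 11/9 split occurred in about 11%, 49% and 49% of trials with 0, 1 and 2 drop-outs. A 12/8 split occurred in 0%, 0% and 2%.

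**Degrees of freedom.** A mixed model on complete pairs matches the two-sample t-test only if the between-participant variance is not estimated at zero and 18 df are used. That estimate was zero in 1.1%, 19% and 50% of simulated trials at an assumed within-person correlation of 0.5, 0.2 and 0. A normal reference in place of 18 df gives type I error 2·P(t18 > 1.96) = 6.6%.

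**The case against.** The paired t-test is a valid analysis here. Its estimate is unbiased over randomisation, and at 10/10 its type I error never exceeds 5%. Choosing between two valid tests is partly preference. That stands, and it limits the weight of this point.

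All the harm rests on assumed period effects, and the striking figure needs a large one. A 2-point effect is about 31 minutes of a 26-hour session (0.02 × 1,560 = 31.2) and 87% of the planned treatment difference (2/2.3). The documents argue against that size. Section 6.1 asks for identical food before the second visit. Section 6.2 calibrates the sensor before closed loop starts and makes the study days the same apart from the control approach. Section 6.2.1 withholds carbohydrate content and meal dose from participants. These measures do not exclude a smaller first-visit effect, so the 0.5- and 1-point rows are the better guide.

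Period may also be one of the unnamed factors. That is why the claim is only that adjustment is not assured. Large imbalance is unlikely, given the low expected drop-out and the rescheduling allowed in section 12. The rule requiring more than 80% of sensor values could add some imbalance, but this was not quantified.

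Finally, the remedy leaves the signed-rank branch unadjusted. That is true. A percentage with adult means of 3.63% and 3.75% (Figure 2) may well be non-normal. The rank-based alternative is a real trade-off, so it is offered only as a sensitivity analysis.

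**Conclusion.** The point holds as a low-severity improvement. The paired tests contain no period term, and the model sentence cannot be run as written and does not secure one. No analysis is invalid and the sample size is sound.

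On an SD of 3.0 without period variation and a 10/10 split, the loss is 0.6 power points at a period effect of 0.5 points (90.2% to 89.6%) and 2.2 at 1 point (90.2% to 88.0%). It reaches 9.7 only at an extreme 2 points (90.2% to 80.5%). If the SD already contains period variation, nothing planned is lost and adjustment gains 2 points at a 1-point effect (93% against 91%). At 11/9, which is about as likely as not once a drop-out has been replaced, the estimate also shifts by a tenth of the period effect. All period effects are assumptions. Adjustment for period does not deal with carry-over.

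**What to change.** In sections 8.2.1.5 and 9.2, when data are normal, make the primary comparison a two-sample t-test, between the two sequences, of each participant's period 1 minus period 2 difference (18 df at N = 20). The treatment difference is half the between-sequence difference, reported with its 95% CI. Alternatively, use a mixed model with treatment and period as fixed effects and participant as random intercept, with the degrees of freedom stated. In the model sentence, replace the outcome and the unspecified adjusting factors by treatment, period and a named list, and say which analysis is primary.

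For non-normal data the signed-rank test may stay primary. A rank-sum test of the period differences between sequences can be an optional sensitivity analysis. In simulation it was about 2 power points lower with no period effect, about level at 1 point, and 9 to 10 points higher at 2 points. Those runs had no ties or zeros, so its cost for this bounded outcome is not known.

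The cost is a change of wording, with N still 20. If there is no period effect, the t-based adjustment loses 0.2 power points at 10/10 (90.2% to 90.0%), 0.5 at 11/9 (to 89.7%) and 1.4 at 12/8 (to 88.8%). If the change is treated as a deviation from the plan, the duty in section 9.2 to inform the authority, the ethics committee and the GCP unit, and to publish both plans, would apply.

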5.2. Exclusion criteria

- Allergy to glucagon or lactose
- Allergy to faster insulin aspart (FiAsp)
- Pheochromocytoma
- Self-reported lack of hypoglycemia symptoms when blood glucose is < 3.0 mmol/l
- Inability to follow study procedures, e.g. exercise, sleeping, blood sampling, and meal intake
- Pregnancy, nursing, plan to become pregnant or sexually active and not using adequate contraceptive methods (intrauterine device, contraceptive pill, patch or injection)
- Use of anti-diabetic medicine (other than insulin), corticosteroids or other drugs affecting glucose metabolism during or within 30 days prior to study participation
- Other concomitant medical or psychological condition that according to the investigator's assessment makes the participant unsuitable for study participation

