At day 1 17:00 the study is initiated, and the closed-loop system takes over glucose control. Except from the control approach (single- vs. dual-hormone), the study days are identical and as depicted in Figure 5. During the study visit, participants can move around freely, but they can only perform actual exercise during the stationary bike exercise session at day 2 16:30. At nighttime, they are encouraged to be in bed and, if possible, sleep. At predefined timepoints, we measure blood pressure and pulse, and we ask them to rate their nausea level on a visual analog scale (VAS) from 1 to 100 to assess possible side effects of glucagon (vomiting rates as 100). In addition, we ask them to self-rate blood glucose levels before bedtime (23:00), upon wake-up (07:00-08:00), before each meal, before exercise, and every 10 minutes during exercise (SOP_worksheet).

Participants are asked to assess the amount of carbohydrate in each of the meals and snack served during the study. These procedures are performed when participants are resting.

Single-hormone and dual-hormone closed-loop control study sessions end 26 hours after study start. The study pumps and the CGMs are disconnected and the participants reconnect their own pumps and CGMs.

The two study sessions are separated by at least 36 hours.

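### Section 10.1 sets the stop level for the 5-minute YSI checks after a low at 3.9 mg/dl; the unit should be mmol/l

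*Combined protocol and SAP*

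**What the plan says.** Section 10.1 starts the procedure with "A hypoglycemia episode is defined as one plasma glucose value < 3.0 mmol/l". The physician then gives oral carbohydrate, and "The treatment will be repeated if the hypoglycemia has not resolved within 15 minutes". No numeric level is given for resolution. The follow-up rule comes next: "Repeated YSI measurement will be performed every 5 minutes until BG is > 3.9 mg/dl", with a reference to SOP_Dysglycemia.

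The next paragraph deals with a different situation, opening with "If at any point during the study the participant experiences symptoms of hypoglycemia and requests oral carbohydrate". There a sample is drawn and carbohydrate is given whatever the value, but "repeated YSI measurements will only be measured if < 3.9 mmol/l".

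Elsewhere 3.9 is always in mmol/l: the exercise rule (6.2.2), the primary outcome (8.2.0) and the YSI outcomes (8.2.1.2). Section 10.2 also states YSI glucose in mmol/l, for example "If an YSI blood glucose value exceeds 14.0 mmol/l". The only other use of mg/dl in the document is for the saline in 7.2.3, which is not a glucose level.

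**The concern.** The trigger and the stop level of one procedure are in different units, and the stop level as printed lies far below the trigger. A rule meant to follow a participant back above 3.9 mmol/l is then satisfied from the outset.

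This is a decision threshold in a safety procedure for participants aged 13 to 17. What is at stake is the close YSI follow-up of lows that the symptomatic-request paragraph does not reach. The exclusion in 5.2, "Self-reported lack of hypoglycemia symptoms when blood glucose is < 3.0 mmol/l", narrows that group but does not deal with sleep. Section 6.2 says of participants "At nighttime, they are encouraged to be in bed and, if possible, sleep", and the Background (section 1) describes non-severe nocturnal lows as very frequent in children and adolescents. A secondary effect is fewer YSI samples during such lows, which bears only on the secondary YSI outcomes in 8.2.1.2.

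**Working it through.** **Inputs**

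- Printed stop level: 3.9 mg/dl (10.1).
- Trigger: below 3.0 mmol/l (10.1).
- Level used elsewhere: 3.9 mmol/l (10.1 next paragraph, 6.2.2, 8.2.0, 8.2.1.2).
- Routine YSI sampling: every 10 to 30 minutes (6.2.3).
- Re-treatment check: 15 minutes (10.1), device not named.
- Night interval: 23:00 to 08:00 (list of intervals at the end of section 8); session length 26 hours (6.2).
- Conversion: about 18 mg/dl per mmol/l. The document does not give this; it is assumed from a molar mass of glucose of about 180 g/mol.

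**Unit conversion**

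- Printed stop level: 3.9 / 18 = 0.217, about 0.22 mmol/l. A factor of 18.02 gives 0.216.
- Trigger: 3.0 × 18 = 54 mg/dl.
- Intended stop level: 3.9 × 18 = 70.2 mg/dl.
- Trigger over printed stop level: 54 / 3.9 = 13.8.
- Intended over printed stop level: 70.2 / 3.9 = 18.

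A value below 3.0 mmol/l that starts the procedure will in practice be above 0.22 mmol/l. The stop condition is therefore met by the triggering sample itself or, if one repeat must be taken first, by that repeat. The printed rule yields 0 or 1 repeat. With mmol/l, the stop level lies above the trigger, as a recovery criterion must.

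**Illustration of the lost sampling**

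Take a low without symptoms or a request that needs 30 minutes to pass 3.9 mmol/l. The duration is assumed, and the routine clock is counted from the triggering sample.

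- Intended rule: 30 / 5 = 6 YSI repeats.
- As printed, routine samples: 30 / 30 = 1 to 30 / 10 = 3.
- As printed, 15-minute check: 1 if it is a YSI reading, otherwise 0.
- As printed, 5-minute rule: 0 to 1.
- Total as printed: 1 + 1 + 0 = 2 to 3 + 1 + 1 = 5. If the 15-minute check is not a YSI reading: 1 + 0 + 0 = 1 to 3 + 0 + 1 = 4.

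Discretionary samples under 6.2.3 would add to these.

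**Night window**

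23:00 to 08:00 is 9 hours, and 9 / 26 = 34.6% of the session. This is the share of time in which sleep could hide symptoms, not a frequency of lows.

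**The case against.** The strongest reply is that nobody would act on the printed value. A recovery level of 0.22 mmol/l after a trigger of 3.0 mmol/l makes no clinical sense, and the next paragraph of 10.1 pairs the same number with the right unit. Section 10.1 also hands the management of lows to SOP_Dysglycemia, so bedside practice depends on a text not supplied here. This stands, and it is why the point is minor. It does not make the sentence right: the next paragraph governs symptomatic requests and leaves the rule for a detected value below 3.0 mmol/l as printed.

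The sleep argument can also be pressed. The series starts only after a low has been detected and oral carbohydrate is being given, so the participant has normally been woken. Sleep may delay detection, but detection does not use this threshold. That is fair, and the 35% should not be read as exposure to the error.

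Other surveillance continues. The CGM sends a value to the study phone every 5 minutes (7.1.6). Staff are always present (10 and 17) and may halt insulin or give glucagon or intravenous glucose (17). What is lost is therefore YSI confirmation, not all glucose monitoring.

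Finally, the sample counts rest on an assumed 30-minute low and on literal compliance. They illustrate scale and are not an estimate of what will happen; no effect on a YSI outcome has been shown.

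**Conclusion.** The concern holds, as a minor error. The stop level in 10.1 carries the wrong unit. It is 18 times below the evident intention and about 14 times below the trigger, and read literally it reduces the 5-minute series to at most one repeat. That conclusion needs only the standard conversion factor, and the intended unit is not in doubt.

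The practical reach is narrow: close YSI follow-up of lows without symptoms or a carbohydrate request, and the density of YSI samples in those lows. Whether it reaches the bedside at all depends on SOP_Dysglycemia. The 15-minute re-treatment rule and routine sampling do not use this value. The primary outcome is defined on CGM at 3.9 mmol/l, so its definition is unaffected, as are the sample size and power.

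**What to change.** In 10.1, replace mg/dl with mmol/l in the sentence on repeated YSI measurement, so that the checks continue until glucose is above 3.9 mmol/l. Confirm that SOP_Dysglycemia states the same level and unit, and correct it if it does not.

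The cost is one word in the protocol and one check of the SOP. Design, sample size and analysis do not change.
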